7.1 Inclusion criteria

All participants must meet the following inclusion criteria:

At time of consent

- 1. Male of female participant with Sickle Cell Disease (any genotype)
- 2. Age 16 or older
- 3. Registered at trial centre with a pre-agreed personal pain management protocol uploaded on their electronic patient record
- 4. At least one attendance with acute pain during the past 2 years
- 5. Able and willing to give informed consent

At time of presentation with APC

- 6. Points 1-5 patient inclusion at time of consent
- 7. Uncomplicated APC requiring acute hospital treatment
- 8. Pain score 5 or more on verbal 0-10 scale
- 9. Confirmed signed consent form

7.2 Exclusion criteria

Any participant who meets one or more of the following criteria will be excluded from participation:

At time of consent

- 1. Participants who are pregnant and more than 16 weeks' gestation
- 2. More than 10 hospital attendances for acute pain management in the past 12 months
- 3. Patient receives regular red-cell-exchanges with HbS levels < 20%

At time of the presentation with APC

- 4. Points 1-2 patient exclusion at time of consent
- 5. Participant has been treated for two pain episodes within the trial protocol.
- 6. Participant has been treated for a pain episode on the trial protocol within 28 days.
- 7. The ACU is open for less than 6 hours from time of presentation
- 7. Additional sickle cell complication as assessed at telephone triage or on arrival by specialist medical and/or nursing staff:
 - g. Acute chest syndrome
 - h. Acute stroke
 - i. Priapism
 - j. Sepsis
 - k. Observations Temp >38.5 degrees, oxygen saturations <94%
 - I. Any other medical issue at the trial team discretion

The PI is responsible for ensuring that all vulnerable participants are protected and participate voluntarily in an environment free from coercion or undue influence.

8. Study design

This study is an open, multicentre randomised trial of participants 16 years or older with SCD.

Potentially eligible patients will be identified at their local trial centres by their care team and referred to their local trial centre study team, which will enable informed consent and confirm eligibility and availability of pain management protocol.

Trial centres will be NHS hospitals where SCD patients are routinely managed, and where ED and Ambulatory Care Unit facilities are both available for managing acute sickle cell pain. As required for standard of care SCD pain management in the NHS, each patient will have a pre-agreed personal pain management protocol uploaded on their electronic patient record, which reflects their usual standard care.

Subjects will be instructed to contact the local site study centre by telephone if unwell with acute pain. This telephone call will be taken by a trial nurse or doctor, who will use a trial algorithm (Appendix 2) to assess whether the patient has an eligible APC. Once this is confirmed, they will take further verbal consent to proceed with the study. The patient will then be randomised and asked to attend either ED or ACU, where they will then receive their routine protocol of care.

Patients will not be randomised if:

1. Pain can be managed without the need for hospital attendance.

2. Symptoms suggest a complicated crisis, where additional medical problems need to be managed.

3. ACU is not available at the trial centre.

The procedure for these different eventualities is illustrated in the flow-chart (Appendix 3).

Randomised patients

For randomised patients, their management will be implemented by their health care team for ED or ACU, using their pre-agreed pain management protocol. The trial team will not be responsible for treating the patient, but will have the following responsibilities:

- Confirmation of consent, eligibility and allocation to correct treatment location
- Pain score (0-10 numeric rating scale) at baseline and hourly for first 6 hours
- Collection of the following data:
 - a) Safety data (respiratory rate and sedation score) hourly for first 6 hours (taken from hospital paper or electronic record. Record actual values and percentage of scheduled measurements.
 - b) Adherence to pre-agreed pain management protocol.
 - c) Cumulative opioid dose over the first six hours (from hospital paper drug chart or electronic prescribing record) and duration of episode in ED or ACU (APC episode resource use CRF).
 - d) Whether the patient is admitted or discharged from ED or ACU.
 - e) Any additional analgesic medication and all non-analgesic medication.
 - f) Health economic data (Section 11.3)

- g) Patient satisfaction questionnaire, taken 14 and 28 days after presentation using the SCAPE questionnaire.
- h) Quality of life assessment; using the EQ-5D-5L tool taken on consent, presentation, 6 hours, 14 and 28 days after the presentation.
- i) Length of stay for patients admitted to hospital. Defined as time from the decision to admit, to time patient leaves ward.
- j) Re-attendance rate (within 7 days).
- k) Complication rate (acute chest syndrome, other acute sickle complications, physician diagnosis from discharge summary).
- I) Education/employment/daily activity loss (social determinants of health assessment).
- m) Resource use CRF including Work Productivity and Activity Impairment Questionnaire, collected at consent, 14 days and 28 days follow-up.

Observational Arm

Consented subject may be triaged with an uncomplicated APC, but cannot be randomised for a number of reasons including:

- No trial staff available
- No available space on ACU
- ACU is closed
- Presenting within 6 hours of closure of ACU

These subjects will be managed according to normal standard care. The trial team will be responsible for a phone call 14 and 28 days after presentation and will collect clinical data the following data:

- Analgesic medication and all non-analgesic medication (from hospital paper drug chart or electronic prescribing record) and duration of episode in ED or ACU (APC episode resource use CRF).
- Quality of life assessment; using the EQ-5D-5L tool taken on consent, presentation, 6 hours and 7, 14 and 28 days after the presentation.
- Education/employment/daily activity loss (social determinants of health assessment).
- Resource use CRF including Work Productivity and Activity Impairment Questionnaire, collected at consent, 14 days and 28 days follow-up.
- Length of hospital admission, if applicable.
- Adverse events (recorded in the clinical notes and discharge summary).

9. Study procedures

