Potential alternatives to current ED care include specialised units providing care in an alternative hospital-based setting. These are variously described as ambulatory units, day care units or infusion centres. For the purposes of this study we refer to them as Specialist Hospital-based Ambulatory Care Units (ACUs). The ASH guideline specified that patients on these units should be managed by a team specialised in acute SCD pain management, and should be located in a hospital with easy access to acute and intensive care facilities, recognising that occasionally patients present with acute pain together with life-threatening complications including acute chest syndrome and sepsis. This type of care provision is generally available during working hours only (Monday to Friday, 9am to 5 pm), although there are some examples of extended opening hours.^{3, 4}. The unit could be entirely dedicated to SCD, or alternatively, with smaller patient populations or insufficient dedicated staff and space, the service could be embedded in a larger multi-specialty unit, such as a hospital-based haemato-oncology unit.^{3, 5}

Currently, there are no randomised studies comparing standard ED care with ACU's, and relatively few observational studies, which are predominantly from a United States health care perspective. Reports in the 1990's from Montefiore Medical Centre, New York, USA⁶, and the Day Centre at Birmingham City Hospital, UK⁷, demonstrated satisfactory pain control, and reduction in hospital admissions, leading to significant cost savings for the service. These finding have subsequently been replicated in other centres such as an infusion clinic at Johns Hopkins Medical Centre and in the paediatric setting^{3, 4, 8, 9}. A report from a day care unit in Jamaica where the unit was not located in a hospital setting highlighted the potential for harm. Fatal events were reported in a small number of patients who had been discharged home, with causes of death including acute chest syndrome and sepsis.¹⁰

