9.6 Schedule of Assessment

See Table 1.

Study event	Screening	Consent and enrollment	Phone triage with APC	ED or ACU with APC	Discharge	Follow up	Follow up						
Study Day			1		1							1.1 douro	20. devie
Study event number	4				1	1	-			10	14	14 days	26 days
	1	4	2 3	4	5	6				10	11	12	13
Study time (nours)				(1	2	: 3	4	+ t	6			
Eligibility	X												
Confirm individual protocol		х	х	х									1
Given patient information sheet	х												1
Informed consent		х											1
Confirm consent			Х										
Demographics ^b		Х											
Medical history ^c		Х	Х										
Confirm inclusion/exclusion criteria			Х										
Confirm eligible APC			Х										
Confirm ED and ACU care available			Х										
Randomisation			Х										
Concomitant medication ^d		Х	Х										
Social determinants of health assessment		Х	Х								Х	Х	Х
EQ-5D-5L °		Х	Х								Х	Х	Х
Satisfaction with care questionnaire ^f		Х									Х	Х	Х
Vital signs ^g				Х	Х	Х	Х	Х	Х	Х	Х		
Pain score ^h				Х	Х	Х	Х	Х	Х	Х	Х	Х	Х
Protocol adherence ⁱ											Х		
Time to. disposition ^j											Х		
Time to readiness for discharge											Х		
Cumulative opiate dose k											Х		
Resource use CRF including Work Productivity and Activity Impairment Questionnaire ^m	r	х									х	x	х
APC episode resource use CRF											Х	Х	Х
Adverse events ⁿ											Х	Х	Х
Length of stay											Х		
Re-attendance												Х	Х
EQ-5D-5L for care givers		Х										Х	Х
Care giver questionnaire including Work Productivity and Activity Impairment Questionnaire		x										x	х

Abbreviations: ED; emergency department, ACU; ambulatory care unit, APC; acute painful crisis.

^a 6 hours, or until discharge if before

^b Age, sex, genotype

^cPast medical history, to include sickle complications

^d Collect information from the paper or electronic drug chart

^e Provide patient with the EQ-5D-5L questionnaire. To complete on presentation and 7 days after presentation.

^f Patient satisfaction questionnaire

^g Hourly for the first 6 hours a per standard of care. These results should be taken from the hospital paper or electronic record. Record actual values and percentage of scheduled measurement

^{*h*} Visual pain score to be taken by dedicated trial team. Score to be taken at baseline and hourly for the first 6 hours

^{*i*} Use the hospital or paper record to confirm adherence to protocol

^{*j*} Was the patient admitted or discharged from ED or ACU

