^{*k*} Cumulative opioid dose over the first 6 hours. Use data from the hospital paper or electronic drug chart.

¹To include, but not limited to; acute chest syndrome, hospital acquired pneumonia, any other significant adverse event CTCAE grade > 3

^m Work Productivity and Activity Impairment Questionnaire

 $^{\it n}$ Record any AEs or SAEs in the 7 days from presentation. Use patient's notes and discharge summary.

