9.10 Data Collection and Follow up for Withdrawn Subjects

A first APC treated in on trial can be used for data analysis if a patient subsequently withdraws consent from continuing in the trial for a second episode.

10. Assessment and management of risk

No investigational medicinal product is being used in this trial. The analgesic drugs and any non-pharmacological agents used to treat pain will be the same as in their standard care protocol. Observations and any bloods tests or diagnostic imaging will be performed as required for standard of care, and will not be part of the trial evaluation. Subjects who would normally access ACU for their care may be randomised to ED care, and this may be perceived by the subject as a worse option. The risks for subjects involved in the study include:

- Trial procedures delaying access to standard care.
- Trial procedures interfering with standard care and with teams implementing. standard protocols in acute care and, for those admitted to hospital, after admission to medical wards.
- Patients being discharged from hospital and not followed up according to standard care protocols once discharged.

In mitigation, both treatment arms incorporate measures to improve on current standard of care during the initial stages of hospital management of acute pain. These include allocation of individualised care plans in both arms of the study (treatment in ED or on ACU), enhanced supervision of the trial subjects, which is anticipated to improve patient safety and satisfaction and reduce harm. Prior to implementation of the trial in trial centres, and during the trial implementation period, there will be regular

training sessions for clinical trial staff and standard care staff, to ensure that trial procedures are correctly implemented.

There will also be an independent trial monitoring committee which will evaluate safety and operational problems during the entire clinical trial implementation period.

11. Statistical considerations

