11.3.2 Assessment of costs

We will identify, measure and value costs across three broad categories.

a) Cost for the treatment of index acute painful crises

This will have two components: cost of treatment in ED or specialist centre and, if relevant, cost of hospitalisation. The first include medication and staff costs for index pain episode treatment and we will undertake a partial micro-costing to ensure consistency in the cost estimates between the two arms. We will cost pain treatment medications used using information on type and volume of medications used and applying national drug tariffs.²⁶ To estimate staff costs, we will collect data on the type and pay band of the professional providing treatment and duration of episode in ED or

ambulatory care for the index pain episodes extracted from hospital electronic systems. In a scenario analysis, we use established unit costs for pain episode treatment in ED, the national schedule unit costs of emergency care to these visits,²⁷ and in ambulatory units, the unit costs of treating patients for acute sickle cell pain under the current commissioning and reimbursement structure of specialised haemoglobinopathy services in the NHS.

The second component is hospitalisation cost. If patients are admitted after initially presenting at ED or ambulatory care unit for treatment of acute pain episode, we will cost these admissions using the case-mix-based reference costs for the respective admissions (HRGs based). For short admissions that do not require overnight stays, we will apply respective day case unit costs and for longer admissions, we will apply the unit cost of non-elective admitted care for sickle cell with crisis.

b) Cost of other health service use

In addition to index acute pain crises treatment costs, we will assess health care resource use and costs associated with outpatient, inpatient or emergency visits and services for sickle cell and, separately, non-sickle cell related health problems. We will consent patients and request linked routine Hospital Episode Statistics (HES) data,²⁸ including inpatient, outpatient, emergency care and critical care episodes for the 28 days period prior to index pain episode (baseline costs) and for the 28 days follow-up period in the study. We will report use of different categories of care and their cost by applying national tariffs to the service use data.

c) Lost productivity and informal care

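### Complications are defined from the discharge summary, so how completely they are captured depends on disposition, which the ACU is expected to change, and Section 6.4 names no safety outcome

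*Protocol*

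**What the plan says.** For randomised patients, Section 8, item (k), lists the "Complication rate (acute chest syndrome, other acute sickle complications, physician diagnosis from discharge summary". It gives no time window. In Table 1 (Section 9.6) the row "Adverse events ⁿ" is marked at discharge, 14 days and 28 days, yet its footnote reads "Record any AEs or SAEs in the 7 days from presentation. Use patient's notes and discharge summary". For the observational arm, Section 8 has "Adverse events (recorded in the clinical notes and discharge summary".

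Section 6.4 makes the proportion admitted, length of stay and fitness for discharge secondary endpoints. It lists no complication, adverse event, death or re-attendance endpoint, although Section 8, items (j) and (k), collects re-attendance within 7 days and complications. Beyond the primary outcome, Section 11.2 promises a between-group comparison for secondary outcomes and leaves full details to a separate SAP.

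The protocol recognises post-discharge harm. Section 5.1 says of a day care unit in Jamaica that "Fatal events were reported in a small number of patients who had been discharged home", with acute chest syndrome and sepsis among the causes. Section 10 lists as a trial risk "Patients being discharged from hospital and not followed up according to standard care protocols once discharged". Section 11.3.2 plans to "request linked routine Hospital Episode Statistics (HES) data" on inpatient, outpatient, emergency and critical care over the 28-day follow-up, for costing.

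**The concern.** The intervention is a place of care, and one of its expected effects is on who is admitted. Section 5.1 cites earlier reports of fewer admissions with day units, and a US observational comparison in which infusion-centre patients were much less likely to be hospitalised. Section 5.2 asks whether admissions can be avoided.

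If a complication counts only when a physician has written it in the discharge summary, the source is more complete for admitted patients than for those sent home. A patient discharged at hour 5 who develops acute chest syndrome on day 2 is not in that summary. A patient still on the ward on day 2 is. A difference in admission can then produce a difference in recorded complications where none exists.

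The trial is meant to inform wider adoption of ACUs. The benefit of fewer admissions is a named endpoint. The corresponding hazard of harm after discharge is not, and it rests on a source that is weakest where the hazard lies.

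**Working it through.** The protocol gives no complication, admission or capture rate, so there is no figure of its own to reproduce on this point. The only figure borrowed from it is the sample size, which does reproduce: adjusted SD = 3.2 × √(1 − 0.5²) = 2.771; about 96.47 per arm for a difference of 1.3 at 90% power; 96.47/0.85 = 113.5, so 114 per arm and 228 in total.

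**Step 1. Is each source independent of disposition?**

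| Route | Where | Independent of disposition? |
|---|---|---|
| Discharge summary | Section 8(k) | No; it closes when the patient leaves |
| Notes and discharge summary | Table 1, footnote n | Partly; notes may show a later visit to the same site, but nothing says they would show care elsewhere |
| AE row at days 14 and 28 | Table 1 | Timing yes, but the footnote fixes the source and a 7-day window |
| Clinical Assessment CRF | Section 14.2, 7–14 days | Possibly; no complication question is specified, and the 28-day list has no such form |
| SAE reporting | Sections 17.4–17.5 | Starts when staff become aware; it is a reporting duty, not a search for events |
| Re-attendance | Section 8(j); Table 1, days 14 and 28 | Collected, but not an endpoint |
| HES linkage | Section 11.3.2 | Yes, but described for costs only |

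Section 17.5 also keeps crisis pain, including hospitalisation for it, off the trial CRF as an adverse event unless it is severe. A pain readmission after early discharge may therefore not be recorded as one.

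**Step 2. How large could the distortion be?** Assume the same true risk *p* in both arms, full capture in admitted patients and capture probability *s* in patients sent home. With admission proportion *a*, the recorded risk is *p*[*a* + (1 − *a*)*s*]. The true risk cancels from the ratio:

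RR(ACU/ED) = [a_ACU + (1 − a_ACU)s] / [a_ED + (1 − a_ED)s]

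| Capture *s* | ED 40%, ACU 20% admitted | ED 50%, ACU 25% admitted |
|---|---|---|
| 0.3 | 0.44/0.58 = 0.76 | 0.475/0.65 = 0.73 |
| 0.5 | 0.60/0.70 = 0.86 | 0.625/0.75 = 0.83 |
| 0.7 | 0.76/0.82 = 0.93 | 0.775/0.85 = 0.91 |
| 1.0 | 1.00 | 1.00 |

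All admission and capture rates here are assumptions.

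In counts, with *p* = 10% and 114 per arm, 11.4 events are expected in each arm. At *s* = 0.3 and 40% v 20% admitted, 114 × 0.058 = 6.6 would be recorded in ED and 114 × 0.044 = 5.0 in ACU.

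**Step 3. What could a safety comparison deliver?** With 114 per arm, power is about 30% for 5% v 10% and 56% for 10% v 20%. At a 5% rate in both arms the 95% interval for the difference has half-width 1.96 × √(2 × 0.05 × 0.95/114) = 5.7 percentage points. It would be an estimate, not a powered test.

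**The case against.** The strongest reply is that the discharge summary is not the only route. Table 1 marks adverse events and re-attendance at 14 and 28 days, footnote n names the notes as well, and Section 14.2 lists a Clinical Assessment at 7–14 days. Section 17.3 has the research team follow up adverse events. Under Sections 17.4–17.5 every SAE, including death, is reported within 24 hours of awareness, and the external committee in Section 19 reviews adverse events. This stands: a reader might infer that events after discharge are lost altogether, and the documents do not support that. What remains is that none of these routes specifies that complications are sought in the same way whether or not the patient was admitted.

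A reader might also infer that harms will never be compared by arm. That does not follow. Section 11.2 defers detail to a SAP that is not at hand and may tabulate safety by arm. But the source and the endpoint list are fixed in the protocol, and a SAP cannot recover events that were not collected.

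A third tempting reading is a much larger distortion. With 45% v 25% admitted and no capture at all in discharged patients, the ratio would be 0.25/0.45 = 0.56. Zero capture conflicts with the routes above, so that figure should not be used.

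Finally, the deaths in Section 5.1 came from a unit outside a hospital, whereas SCAPE 2 sites are hospitals with both ED and ACU, and the Section 10 risk is not specific to one arm. Both show that the protocol regards post-discharge harm as relevant; neither shows that it will occur more often with the ACU.

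**Conclusion.** The point holds as a weakness in how complications are ascertained, not as a demonstrated bias. The defining source in Section 8(k), and the sources in footnote n, make capture depend on disposition. If the ACU discharges more patients, the likely direction is in its favour.

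Under the assumed ranges, an equal true risk would appear as a risk ratio of about 0.73 to 0.93. This rests on full capture in admitted patients and on admission and capture rates that the protocol does not give, and the bias vanishes with complete capture. In counts the distortion is one or two events at a 10% risk, within chance variation for a trial of this size. The concern is therefore a misleading safety statement rather than a false significant result. The primary pain analysis is not affected.

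Two textual points need no assumption: Section 6.4 names no safety outcome, and a 7-day footnote is attached to a row marked at 14 and 28 days. The footnote could mean that later contacts only collect events from the first week, or the window could be an error. As written, events after day 7 may be lost.

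**What to change.** 1. In Section 8(k) and footnote n, replace the discharge summary as the defining source with identical ascertainment in both arms to 28 days. Use a fixed complication and readmission question set at the existing day-14 and day-28 contacts, trial-site records including vital status, and the HES extract already requested for costs.
2. In Section 6.4, name complications, unplanned re-attendance or readmission, and death to 28 days as secondary safety outcomes. Report them by randomised arm as estimates with 95% confidence intervals, and say that the trial is not powered to test them.
3. Reconcile the 7-day window in footnote n with the 14- and 28-day columns of the adverse event row.

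The cost is protocol and CRF wording, plus consent and data-request wording so that HES may serve a second purpose. No extra contacts or patients are needed. HES arrives late, so it serves the final analysis rather than live monitoring. The HES components listed in Section 11.3.2 do not name mortality data, so deaths must come from the contacts and site records.
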